### 3.4 Changes in the conduct of the study compared to the protocol

The key compliance/adherence measure during the study is 24-hour urine measurement of volume and osmolality. After the start of study treatment at V3, 24-hour urine is collected at V4 (3 weeks), V5 (3 months), V6 (6 months), V7 (9 months) and V8 (12 months). Apart from the main “intention to treat” analysis, we will perform “per protocol” analysis in which we exclude subjects with major protocol deviations (i.e. whose values of 24-hour urine displays major deviation from expected, given treatment assignment, with those limits defined below (see protocol deviations)).

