#### Intention to treat

The “Intention-to-Treat” population: all randomized study subjects with at least two during study fasting plasma glucose measurements will be analyzed in intention to treat analysis (i.e. regardless of any protocol deviations). This analysis set includes the evaluation of primary and secondary outcomes as well as adverse events (AE) and serious adverse events (SAE) between intervention and control group.

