#### Per protocol

The key protocol deviation that can influence the therapy tested (increased water intake vs control) is that the study subjects do not adhere to the assigned therapy (do not increase water intake in active group / increase water intake in control group). Generally, unless a study treatment is directly administered by study personnel (for example short-term intravenous pharmacological infusions in the inpatient setting) it is impossible to fully control the adherence to the study therapies as study subjects administer the study therapies themselves at home. This limitation is thus the same as in randomized drug trials, where “pill counting” is the most common way to assess compliance/adherence. Whereas the “intention to treat” analysis, which is the primary method, tests if the assigned therapy works regardless of adherence, the secondary “per protocol” analyses will take into account the best available measure of compliance to the current therapy, which is changes of 24-urine measures during follow-up in comparison with baseline. In these per protocol analyses, we will exclude study subjects who, based on values of their 24-hour urine, show indications of poor compliance.

The exclusion of patients let to define the Per-Protocol Set will be based on the urine volume and concentration. These parameters will be considered as the main protocol deviation criteria. Cut-offs for inclusion in the per protocol analysis are at least one of the two criteria below met for 24h UOsm OR UVol:

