**Delta 24h UOsm (Baseline vs. 3 months, 6 months, 9 months and 12 months):**

- Control Group: Those with a decrease in delta 24h UOsm not greater than 25% from baseline.
- Intervention group: Those with a decrease in delta 24h UOsm of at least 50% from baseline.

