### 5.1.3 Populations

We expect a final study sample for intention to treat analysis of at least n=544 evaluable study subjects who have completed the protocol (i.e. with at least 2 fasting glucose measurements, meaning at V3 and at either V6 or V8 or at both V6 and V8). We expect a dysbalance in the final study sample (46% intervention vs 54% control therapy) due to dysbalance in the drop-out rate between intervention and control groups.

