#### 5.4 Study conducts parameters

Variable name	Variable source 	Type 	Unit	Set 
Compliance parameters (markers of urine concentration)				
V6 vs V3 urine osmolality difference (paired test)	D	C	mosm/kg	ITT, PP
V8 vs V3 urine osmolality difference (paired test)	D	C	mosm/kg	ITT, PP
V6 vs V3 urine volume difference (paired test)	D	C	mosm/kg	ITT, PP
V8 vs V3 urine volume difference (paired test)	D	C	mosm/kg	ITT, PP

1. (R)aw or (D)erived data
2. (C)ontinuous or (O)rdinal or (N)oinal
3. Intention to treat (ITT) or Per Protocol (PP)

Study conduct parameter derivations:

Study duration (days): time between the last visit (V8) and randomization visit  
 $= (\text{Date of V8} - \text{Date of V3}) + 1$  will be detailed.

Compliance to study urine volume (see paragraph 5.4 above): This will be used to assess compliance in per protocol analysis.

Time between study visits (days): time between each study visit planned in the study.  
 $= (\text{Date of Vy} - \text{Date of Vx}) + 1$  with  $y > x$ . It will be calculated between V3 – V6, V6 – V8 and V3 – V8 and presented.

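### SAP 5.4 tests urine change in a per-protocol set selected on that change, and its compliance summary leaves out pre-V6 leavers and three collected visits

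*SAP*

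**What the plan says.** SAP section 5.4 lists four compliance rows: the V6-minus-V3 and V8-minus-V3 differences in urine osmolality and in urine volume, each with a paired test. The last osmolality row reads "V8 vs V3 urine osmolality difference (paired test". All four carry the set label ITT and PP.

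Section 4.1 defines the PP set by the same measurements. The entry rule is "Cut-offs for inclusion in the per protocol analysis are at least one of the two criteria below met for 24h UOsm OR UVol". For osmolality, the water arm needs "Those with a decrease in delta 24h UOsm of at least 50% from baseline" and the control arm "Those with a decrease in delta 24h UOsm not greater than 25% from baseline". For volume, the water arm needs a rise of at least 1000 mL and the control arm a rise of no more than 500 mL. Changes at 3, 6, 9 and 12 months are named. The plan does not say whether the rule must hold at one visit, at all of them or on average.

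The ITT set is "all randomized study subjects with at least two during study fasting plasma glucose measurements". Section 5.1.3 explains this as a value at V3 plus one at V6 or V8. Section 3.4 names 24-hour urine as the key adherence measure and states that "24-hour urine is collected at V4 (3 weeks), V5 (3 months), V6 (6 months), V7 (9 months) and V8 (12 months". On the expected evaluable sample, section 5.1.3 says: "We expect a dysbalance in the final study sample (46% intervention vs 54% control therapy".

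**The concern.** The intervention is a behaviour, so the glucose result can be read only beside a fair account of how much extra water was taken. If glucose does not differ between arms, the reader must choose between water that was taken and had no effect, and water that was largely not taken.

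A highly significant fall in osmolality in the PP set points to the first reading, yet the entry rule produces such a fall whatever the arm as a whole did. There is a second, weaker issue. The ITT rows begin at V6 and cover only people with a glucose value at V6 or V8. The early urine of those who left sooner is collected but appears nowhere in the 5.4 summary, and the SAP expects more of these leavers in the water arm.

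**Working it through.** **1. The plan's own figure.** Inputs from SAP 3.3: difference 0.14 mmol/L, SD 0.58 mmol/L, two-sided 5%, 80% power. Per group, n = 2 × (1.96 + 0.8416)² × 0.58² / 0.14² = 2 × 7.849 × 17.163 = 269.4, so 270, as stated. With a 46:54 split, control n = (1 + 54/46) × 7.849 × 17.163 = 292.9, so 293; water n = 293 × 46/54 = 249.6, so 250. The total is 543 against the stated 544 (power 80.1% at 544). The evaluable water arm is thus about 250.

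**2. Does PP selection alone create a urine change?** Simulation with no effect of assignment. From the documents: eligibility (osmolality above 600 mOsm/kg, volume below 1.5 L), the PP cut-offs and four follow-up visits. Assumed, because the documents give no urine variances: median volume 1.3 L and median daily solute 850 mOsm before selection; log-scale SD of solute 0.20 between and 0.15 within persons; log-scale SD of volume 0.25 between and 0.25 within persons (A), or 0.30 and 0.35 (B). As the visit rule is unstated, three readings were tried. Under the any-visit reading, a control must comply at every visit.

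| Scenario, visit rule | Water arm passing PP | V8 volume change: all eligible / water PP / control PP (L) | V8 osmolality change: all eligible / water PP / control PP (mOsm/kg) |
|---|---|---|---|
| A, V8 only | 8.8% | +0.17 / +0.87 / +0.05 | −100 / −635 / −28 |
| A, any visit | 24.8% | +0.17 / +0.46 / 0.00 | −100 / −371 / +20 |
| A, mean of visits | 2.8% | +0.17 / +0.75 / +0.11 | −100 / −718 / −62 |
| B, V8 only | 18.3% | +0.27 / +1.08 / +0.02 | −148 / −740 / +10 |
| B, any visit | 45.0% | +0.27 / +0.56 / −0.05 | −148 / −404 / +99 |
| B, mean of visits | 9.3% | +0.27 / +0.95 / +0.13 | −148 / −784 / −43 |

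The PP arms separate although nobody drank more. The change among all eligible subjects is regression to the mean after selection on concentrated urine; it is equal in both arms.

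For the paired test itself, with 250 water-arm subjects and a within-person log SD of volume of 0.20–0.35: under the V8-only reading, 4–18% pass, the mean osmolality fall is 55–59%, and P<0.05 in 98–100% of runs. Under the any-visit reading, the V8 osmolality and volume tests were significant in all runs. Under the mean-of-visits reading, the osmolality test was significant in 73% of runs (lowest variability) to 100%; the lower figure is sensitive to the assumed noise because so few subjects pass.

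**3. How large is the loss from the ITT rows?** With 1:1 allocation and control loss c, water loss = 1 − (1 − c) × 46/54.

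- c = 0: 14.8%
- c = 10%: 23.3%
- c = 20%: 31.9%

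SAP 6.3 describes drop-out between V2 and V3 as balanced. If equal numbers start, the same formula therefore applies to losses after V3.

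**4. What could that do to the adherence figure?** If leavers had no urine change, the mean among stayers exceeds the mean among all by 1/(1 − loss): 1.17, 1.30 and 1.47 for the three cases. If leavers changed as much as stayers, the factor is 1.00.

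An intermediate illustration, with every adherence figure assumed: 60% of the water arm gain 1.2 L and 40% gain 0.2 L, so the mean among starters is 0.6 × 1.2 + 0.4 × 0.2 = 0.80 L. At 80% overall retention (the protocol's 20% drop-out), water-arm retention is 2 × 0.80 × 0.46 = 73.6%.

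- 10% of adherers and 51% of the others leave: (0.54 × 1.2 + 0.196 × 0.2) / 0.736 = 0.93 L
- 20% and 36% leave: (0.48 × 1.2 + 0.256 × 0.2) / 0.736 = 0.85 L
- Half of the 20% drop-out falls before V3, with 10% of adherers leaving afterwards: retention from V3 is 2 × (0.80/0.90) × 0.46 = 81.8%, and the mean is (0.54 × 1.2 + 0.278 × 0.2) / 0.818 = 0.86 L

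**The case against.** The strongest reply concerns the ITT rows. The primary glucose analysis uses the same set, so urine change in that set is the matching measure of exposure for the glucose comparison. People who stayed but did not drink are in both; people who left before V6 are in neither. Replacing ITT by all V3 attenders would report exposure in a different population from the effect. This stands: the wider set should be added, not substituted.

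Second, the SAP is open about the PP definition, calls PP secondary, and uses the same set label throughout its variable tables. Section 5.1.2 commits to counts per arm of subjects with a compliance deviation, and sections 5.1.1 and 5.8 to attendance and drop-out counts. If only a small share of the water arm reached PP, that would be visible. This also stands, and it limits the harm. But counts do not show what leavers drank, and they do not make the PP urine tests informative.

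Third, V5 and V7 urine is not wholly unused, because the PP rule refers to 3 and 9 months. True, but the 5.4 summary omits both, and V4 as well.

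A reader might infer that adherence is guaranteed to look good in PP and overstated in ITT, so that neither set can show how much water was taken. The documents do not support that. Subjects may qualify on either marker, and the visit rule is unstated, so no single PP test is certain to be significant. The ITT set is not selected on urine, and nothing in the documents says what leavers drank.

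**Conclusion.** The point holds for the PP rows and conditionally for the ITT rows. The PP tests are circular: the tested variables are the entry criteria, and selection alone gives a large and usually significant change. The circularity follows from the text. Its size rests on assumed urine variability and on the reading of the visit rule.

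The ITT rows correctly describe exposure in the set used for the glucose analysis. As a measure of adherence to the assigned therapy they may be too favourable, since at least 14.8% of the water arm is expected to be lost. The possible overstatement runs from none, if leavers drank as much as stayers, to a factor of 1.17–1.47 if leavers had no change and control loss is 0–20%. No primary or secondary outcome test is affected; what is affected is the reading of the glucose result, above all a null one.

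**What to change.** In SAP 5.4:

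- Delete the PP paired tests of urine osmolality and volume, or label them as a description of the selection rule from which no adherence conclusion is drawn.
- Keep the ITT rows.
- Add urine osmolality and volume change by arm and visit, V4 to V8, with 95% confidence intervals, for all subjects who attended V3. One mixed model can do this. It would use the early values of people who later left, and should state its missing-at-random assumption. People who left before V4 have no follow-up urine and should be counted separately.
- Show both arms side by side, because regression to the mean alone moves urine in each arm.
- Report the number and share per arm meeting the PP rule, with all who attended V3 as denominator. Section 5.1.2 already implies the counts. State the visit rule.

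The cost is SAP wording and one extra model on urine already scheduled for collection, with no change to study procedures. The adherence figure may come out less favourable.

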#### 5.5 Prior / Concomitant medications

Variable name	Variable source 	Type 	Unit	Set 
Concomitant medications of relevance at baseline (visit 3)				
Antihypertensive medications a	R	N	Yes/no	ITT, PP
Oral anti-diabetic medications b	R	N	Yes/no	ITT, PP
Lipid lowering medications c	R	N	Yes/no	ITT, PP

a Defined as use of medications included in ATC-groups C02, C03, C07, C08 or C09.

b Defined as use of medications included in ATC-group A10

c Defined as use of medications included in ATC-group C10

1. *(R)aw or (D)erived data*
2. *(C)ontinuous or (O)rdinal or (N)ominal*
3. *Intention to treat (ITT) or Per Protocol (PP)*

## 5.6 Analysis of primary criteria

### 5.6.1 Description of primary outcome measure

The primary outcome measure is between group comparison of the change from baseline to 12-month of fasting plasma glucose.

Variable name	Variable source 	Type 	Unit	Set 
Change of fasting plasma glucose from baseline to 6-and 12-months	D	C	mmol/L	ITT, PP

2. *(R)aw or (D)erived data*
4. *(C)ontinuous or (O)rdinal or (N)ominal*
5. *Intention to treat (ITT) or Per Protocol (PP)*

### 5.6.2 Analysis of primary outcome parameters

The primary analysis (intention-to-treat) will compare the between study groups (intervention vs control treatment) LS-means differences on the changes from baseline to 12 months and from baseline to 6 months in fasting plasma glucose. The main analysis will be based on a linear mixed model with fasting plasma glucose change from baseline to study visits where it is measured during the study (6 and 12 months) as dependent variable. This model produces unbiased estimates under the assumption that missing data are missing at random. The model will be adjusted (through fixed effects) for sex (because of the stratified randomization), baseline value of fasting plasma glucose, treatment, study visit and interaction between treatment and study visit. We will in the mixed regression analysis model within-patient correlation to decrease exponentially with number of days between measurements or through an AR(1) model. The choice of correlation structure specifies the variance-covariance matrix in the mixed regression model. The choice of covariance structure rests on principles of parsimony, simplicity and prior beliefs, rather than post-analysis testing. Model assumptions will be assessed through visual inspection of plots of suitable regression residuals. The estimated LS-mean differences between treatment levels for the change in fasting plasma glucose from baseline to 12 months and baseline to 6 months, the corresponding 95% confidence intervals (CIs) and p-values will be provided. The same analyses will be conducted on the imputed data set (see “Missing Data” sub-section under section 4.1) and the per protocol data set. The analyses will be conducted using SAS PROC MIXED.

Sensitivity analysis as described in Section 4.1, part “Missing Data” could be performed. Conclusions regarding the inclusion of baseline characteristics in the linear mixed model will be based on clinical significances.

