Data handling: The case report form (eCRF) of the present study consists of two separate databases, Redcap and Vattenstudien Content Management System (V-CMS). The questionnaire based data and 4-day web-based dietary and fluid intake data will be electronically stored in the Redcap database, using code linkage. The V-CMS is built to manage bookings, laboratory analyze results, follow-up documentation and study logging. The laboratory results from the hospital clinical chemistry are automatically imported into the V-CMS when analyses are available and validated using logical computerized checks on the data. Data that does not match valid patterns, reference values and/or expected criteria has to be validated manually by authorized nurse before assigned to patient data. All analyzed results, both external and locally generated, are subject for manual input/modification if needed. Anthropometric data, blood pressure and data on p-glucose and urine osmolality (which is analyzed on site and not sent to the lab) are entered manually into the V-CMS. All data are stored in a procedural database and the V-CMS also contains (backend-to-backend) export of data when required.

Archiving of data: Data is archived for at least 10 years.

Sample size: The primary outcome measure for the power calculation is the difference between active and control treatment *in the change of fasting plasma glucose between baseline and 12 months*. We use prior effect estimates from the largest RCT for diabetes prevention study in Europe, i.e. the Finnish Diabetes Prevention Study (FDPS) (New Engl J Med 2001;344:1343-50), which compared individual life style counselling (active treatment) with general oral and written life-style advice (control treatment) in relation to risk of new onset type 2 diabetes and change of plasma glucose concentration and found a 58% decreased relative risk of diabetes. After 12 months, the fasting glucose in the active treatment group was reduced by 4±12 mg/dL vs a 1±12 mg/dL increase in the control group with the mean difference of 5 mg/dL of the 12-month change of fasting glucose being highly significant (P<0.001). **To obtain sufficient statistical power to detect a clinically significant effect size, we base our power calculation on an effect of water vs**

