### 3.3 Sample size

The primary outcome parameter is the difference between active (=extra water) and control treatment in the change of fasting plasma glucose between baseline and 12 months. We use prior effect estimates from the largest RCT for diabetes prevention study in Europe, i.e. the Finnish Diabetes Prevention Study (FDPS) (New Engl J Med 2001;344:1343-50), which compared individual life style counselling (active treatment) with general oral and written life-style advice (control treatment) in relation to risk of new onset type 2 diabetes and change of plasma glucose concentration and found a 58% decreased relative risk of diabetes. After 12 months, the fasting glucose in the active treatment group was reduced by  $4 \pm 12$  mg/dL vs a  $1 \pm 12$  mg/dL increase in the control group with the mean difference of 5 mg/dL of the 12-month change of fasting glucose being highly significant ( $P < 0.001$ ).

To obtain sufficient statistical power to detect a clinically significant effect size, we base the power calculation on an effect of water vs control that is at least 50% of what is considered an epoch changing effect of lifestyle i.e., the difference observed in the FDPS, while assuming the standard deviation for the change ( $s = 0.67$  mmol/L) as observed in FDPS. To be able to detect  $\geq 50\%$  of that effect (a difference of 2.5 mg/dL = 0.14 mmol/L between treatments in 12-month change) we need 319 evaluable subjects in both the active and control treatment group at a power of 80% and a 2-tailed significance level of =0.05, a total of 638 evaluable subjects. As the glucose measurement in the study used a more recent and exact method, the standard deviation of the change of glucose was recalculated by the DSMB in October 2022 from the first completed 357 study participants ( $s = 0.58$  mmol/L). With this smaller standard deviation, the power (with all other assumptions unchanged) was 270 evaluable subjects per group, i.e.  $n=540$  evaluable subjects in total. When also taking into account a dysbalance (with slightly higher drop-out rate in subjects in the intervention group), a total of 544 evaluable subjects were estimated to be needed for 80% power.

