## 6 Statistical analyses

### 6.1 Hypothesis and significance level

- The primary and secondary outcomes will be tested using two-sided tests ( $P<0.05$ ) with the hypothesis that there will be a significant difference in the change of the outcome parameter between intervention and control group at  $P<0.05$  level in a 2-sided test.

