## 6.4 Handling multiple testing

No multiplicity adjustment strategy is planned.

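### The SAP should name the 12-month contrast as the single primary test: the 5.6.1 table and section 5.6.2 put the 6-month contrast beside it without a hierarchy

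*SAP*

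**What the plan says.** Several places point to 12 months alone:

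- The protocol's Outcome paragraph defines continuous outcomes as the 12-month value minus baseline, with fasting glucose as primary. Its Sample size paragraph rests on the treatment difference "in the change of fasting plasma glucose between baseline and 12 months".
- SAP 3.3 repeats this. Its target difference of 0.14 mmol/L is for the 12-month change, and SAP 7 gives the revised SD of 0.58 mmol/L as the value at month 12.
- The sentence that opens SAP 5.6.1 reads: "The primary outcome measure is between group comparison of the change from baseline to 12-month of fasting plasma glucose".

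Two places bring in 6 months under the primary label:

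- The table directly below that sentence lists the variable as "Change of fasting plasma glucose from baseline to 6-and 12-months".
- SAP 5.6.2 defines the primary intention-to-treat analysis as a comparison of "LS-means differences on the changes from baseline to 12 months and from baseline to 6 months in fasting plasma glucose". It then promises inference at both visits: "baseline to 12 months and baseline to 6 months, the corresponding 95% confidence intervals (CIs) and p-values will be provided".

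Nothing else in the SAP settles the matter. Section 6.1 says "The primary and secondary outcomes will be tested using two-sided tests" at P<0.05 and names no deciding contrast. Section 6.4 says: "No multiplicity adjustment strategy is planned". Section 7, which lists departures from the protocol, mentions only the sample size.

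**The concern.** Fitting both visits in one mixed model is sound, and a model with a treatment-by-visit term naturally yields one contrast per visit. The difficulty is that both contrasts carry the primary label and neither is ranked. Suppose the 6-month contrast gives p<0.05 and the 12-month contrast does not. A report that followed 5.6.2 to the letter could present this as a positive result of the primary analysis. A report that followed the 5.6.1 sentence would call the same trial negative on its primary outcome. An SAP should remove that choice before the arms are compared.

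Two other details blur the focus on 12 months. SAP 5.1.3 counts a participant as evaluable with a baseline value and a value at either later visit, so someone with only a 6-month follow-up value counts toward the 544. The secondary table in 5.7.1 lists fasting glucose again, at 6 and 12 months, so the 6-month change appears under both the primary and the secondary heading.

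**Working it through.** **Step 1. Which contrast was the trial sized for?** Inputs from SAP 3.3, 5.1.3 and 7: difference 0.14 mmol/L in 12-month change, SD 0.58 mmol/L at month 12, two-sided alpha 0.05, power 80%, final split 46% intervention and 54% control.

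- Equal groups: n per group = 2 × (1.960 + 0.842)² × (0.58/0.14)² = 2 × 7.849 × 17.163 = 269.4, rounded up to 270. This matches the SAP.
- Split 54/46: n in control = (1 + 54/46) × 7.849 × 17.163 = 292.9, rounded up to 293. The total is 293/0.54, about 543, against 544 in the SAP.
- Power with 544: the groups are 293.76 and 250.24, so SE = 0.58 × √(1/293.76 + 1/250.24) = 0.0499. Then 0.14/0.0499 = 2.806, and Φ(2.806 − 1.960) = 80.1%.

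The plan's own figure therefore reproduces as one 12-month test at the full 0.05. No alpha is left for a second primary test.

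**Step 2. Type I error under each reading.** If the 12-month contrast alone decides, the error is 5.0%, however many other contrasts are displayed.

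If p<0.05 at either visit counted as success, the error would be 1 − P(|Z₁| < 1.96 and |Z₂| < 1.96), where Z₁ and Z₂ are bivariate normal with correlation ρ. With ρ = 0 this is 1 − 0.95² = 9.75%. SAP 5.6.2 gives only the form of the within-patient correlation (exponential decay or AR(1)) and no value, so ρ is an assumption and the range is shown:

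| ρ between the two test statistics | Chance of at least one p<0.05 under no effect |
|---|---|
| 0 | 9.75% |
| 0.3 | 9.5% |
| 0.5 | 9.1% |
| 0.6 | 8.7% |
| 0.7 | 8.3% |
| 0.8 | 7.8% |
| 0.9 | 7.0% |

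**Step 3. What a genuine two-visit primary would cost.** As an illustration, take Bonferroni at 0.025 per visit:

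- n per group = 2 × (2.241 + 0.842)² × 17.163 = 326.3, rounded up to 327, against 270.
- With 544 subjects split 54/46, power for the 12-month test is Φ(2.806 − 2.241) = 71.4%.

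The planned sample therefore fits a single 12-month primary test and does not fit a pair of co-equal tests with error control.

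**The case against.** The best reply is that 12 months is plainly the primary time point. Every sentence that defines the outcome says so, the effect size, SD and sample size all refer to it, and SAP 7 records no change of primary outcome. The table wording may be a house pattern: SAP 5.7 defines the secondary outcomes by their change to 12 months, yet the 5.7.1 table is headed with 6 and 12 months. On that view the 5.6.1 table only describes the dependent variable of the repeated-measures model. The statement about intervals and p-values would then be about reporting and would set no success criterion. The absence of a multiplicity strategy fits a single primary test, which needs none.

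Most of this stands, and it limits the point. A reader might infer from 5.6.2 and 6.4 that the primary false-positive rate is 8% to 9% as the plan is written. The documents do not support that. No text says that success at either visit is enough, and under the 12-month reading the rate is 5.0%. The 8% to 9% figure needs an either-visit rule and also a correlation of roughly 0.5 to 0.75, which neither document gives.

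The reply does not remove the conflict. Section 5.6.2 is the section an analyst will follow. It defines the primary analysis by two contrasts and does not say that one is supportive. That 12 months was probably meant is a reason to write it down.

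**Conclusion.** The SAP is inconsistent on its primary contrast, and the inconsistency lies in the primary analysis section itself. It is a conflict between stated texts that leaves room for choice after the results are known. It does not show that the trial's type I error is inflated. The error is 5.0% if 12 months alone decides. It would be 7.0% to 9.75% if either visit could count, for assumed correlations from 0.9 down to 0. The correction should be made because it settles in advance how a split result is to be reported, and it costs almost nothing. Confidence is high on the textual conflict. The inflated range is conditional throughout.

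**What to change.** Before the arms are compared:

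1. In SAP 5.6.2, state that the single primary test is the treatment LS-mean difference in fasting plasma glucose change at 12 months, from the planned mixed model in the intention-to-treat set, at two-sided 0.05.
2. In the 5.6.1 table, give the 12-month change as the primary variable. If both visits are listed because the model uses both, say so in a note.
3. Keep the 6-month contrast in the model and report it with its estimate and interval, labelled secondary or supportive.

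This takes about two sentences and one table cell. The model, the 544 evaluable subjects, the 80% power and the data collection are unchanged. The only downside is that a 6-month result cannot be claimed as a primary finding.
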